4.4. Protocol Deviations

In Section 3.1.4, PK analysis set definition is slightly different from protocol amendment 3 Section 8.2.1.3 Pharmacokinetics: The PK analysis set will include all subjects who are enrolled and have received at least one dose of study drug, and for whom concentration data of analytes [SOF, LDV, and metabolite(s), as appropriate] are available. The rationale for this change in PK analysis set definition in SAP from protocol is because if there is concentration record for a subject but is not usable for POP PK modeling, this concentration record is considered no value for PK interpretation.

A summary of important protocol violations will be provided by the Clinical Operations group for subjects in the safety analysis set.

5. BASELINE DATA

5.1. Demographics and Baseline Characteristics

The following subject demographic and baseline characteristics will be summarized by prior treatment experience (treatment naive and treatment experienced subjects) for China and Overall (i.e., China plus Korea plus Taiwan) using descriptive statistics (sample size, mean, standard deviation, median, Q1, Q3, minimum and maximum) for continuous data and by the number and percent of subjects for categorical data. Variables to be summarized include the following:

- age (on date of first dose of study drug) as a continuous variable and for categories (< 65 years, \geq 65 years)
- sex (male, female)
- race and race subcategory (Chinese, Korean, Taiwanese and Other)
- ethnicity (Hispanic or Latino, non-Hispanic or Latino)
- body mass index as a continuous variable and for categories (< 25 kg/m² and \geq 25 kg/m²)
- HCV genotype subtype
- cirrhosis (cirrhosis, absence of cirrhosis)
- IL28B (CC, Non-CC (CT, TT))
- baseline HCV RNA as a continuous variable and for categories (<800,000 IU/mL, \geq 800,000 IU/mL) and (< 5 log₁₀ IU/mL, \geq 5 log₁₀ IU/mL)
- baseline ALT as a continuous variable and for categories (\leq 1.5 x ULN, > 1.5 x ULN)
- response to prior HCV treatment (nonresponse, relapse/breakthrough, IFN intolerant) for treatment experienced subjects
- interferon eligibility (IFN eligible, IFN ineligible, IFN unwilling) for treatment naive subjects
- estimated glomerular filtration rate (eGFR) using the Cockcroft-Gault equation

Age is calculated as the integer of age in years at first dose of study drug. eGFR will be calculated by the Cockcroft-Gault method: $eGFR_{CG}$ (mL/min) = [(140 - age (yrs)) \times weight (kg) \times (0.85 if female)] / (serum creatinine (mg/dL) \times 72), where weight is total body mass in kilograms.

The summary of demographic data and baseline characteristics will be provided for the safety analysis set.

5.2. Medical History

General medical history (ie, conditions not specific to the disease being studied) data will be listed only. General medical history data will not be coded.

6. EFFICACY ANALYSES

6.1. Primary Efficacy Endpoint

6.1.1. Definition of the Primary Efficacy Endpoint

The primary efficacy endpoint is SVR 12 (HCV RNA < LLOQ 12 weeks after discontinuation of all study drugs) in the FAS population. The COBAS[®] AmpliPrep/COBAS[®] TaqMan[®] HCV Test v2.0 will be used to determine HCV RNA results of China in this study. The LLOQ of the assay is 15 IU/mL.

The COBAS[®] Taqman[®] HCV Test v2.0 for use with the High Pure System was used to measure HCV RNA of Korea and Taiwan. The LLOQ of the assay was 25 IU/mL.

6.1.2. Primary Analysis of the Primary Efficacy Endpoint

The primary efficacy analysis described below will compare the observed SVR12 rate for the investigational regimen (i.e., LDV/SOF FDC for 12 weeks) versus the adjusted historical SVR null rate in treatment-naïve, Chinese subjects only.

In addition, a point estimate with a two-sided 95% exact confidence interval using the binomial distribution (Clopper-Pearson method {Clopper 1934}) will be constructed for the SVR12 rate by prior treatment experience for China and Overall (i.e., Korea, Taiwan and China).

Treatment Naïve Subjects

In the primary efficacy analysis the SVR12 rate from China will be compared to the adjusted historical SVR null rate of 57% (as calculated in Appendix 3) using a two-sided exact one-sample binomial test.

The hypothesis for superiority in China is:

H0: SVR12 rate = 57%,

H1: SVR12 rate \neq 57%.

Treatment Experienced Subjects:

There is no treatment option available in China, Korea or Taiwan for treatment experienced patients with GT-1 infection. In the absence of effective antiviral therapy, spontaneous clearance of the HCV is rare. Consequently a nominal SVR rate of 5% is assumed for treatment-experienced subjects.

No statistical hypothesis testing will be performed in treatment experienced subjects. For China and Overall (i.e., China plus Korea plus Taiwan), a point-estimate with two-sided 95% exact confidence interval using the binomial distribution (Clopper-Pearson method) will be constructed for the SVR12 rate.

6.1.3. Subgroup Analysis of the Primary Efficacy Endpoint

Point estimates and 95% exact confidence intervals of the SVR12 rates by prior treatment experience for China and Overall (i.e., China plus Korea plus Taiwan) will be displayed for each subgroup outlined in Section 3.4. The 2-sided 95% exact confidence intervals will be based on Clopper-Pearson method {Clopper 1934}.

A Forest plot will graphically present estimates and 95% confidence intervals of SVR12 rates for each of the subgroups.

6.2. Secondary Efficacy Endpoints

6.2.1. Definition of Secondary Efficacy Endpoints

Secondary efficacy endpoints include the following:

- The proportion of subjects who attain SVR at 4 and 24 weeks after stopping therapy, defined as HCV RNA < LLOQ 4 and 24 weeks after stopping treatment (SVR 4 and SVR 24)
- The proportion of subjects with HCV RNA below LLOQ by study visit
- HCV RNA (\log_{10} IU/mL) and change from baseline in HCV RNA (\log_{10} IU/mL) through Week 12 for China only
- The proportion of subjects with virologic failure as the following:
 - On-treatment virologic failure
 - 1) HCV RNA \geq LLOQ after having previously had HCV RNA < LLOQ, while on treatment, confirmed with 2 consecutive values (note: second confirmation value can be posttreatment), or last available on-treatment measurement with no subsequent follow up values (ie breakthrough)
 - 2) $> 1 \log_{10}$ IU/mL increase in HCV RNA from nadir while on treatment, confirmed with 2 consecutive values (note: second confirmation value can be posttreatment), or last available on-treatment measurement with no subsequent follow up values (ie rebound)
 - 3) HCV RNA persistently \geq LLOQ through 8 weeks of treatment (ie. nonresponse)
 - Relapse
 - 1) HCV RNA \geq LLOQ during the posttreatment period having achieved HCV RNA < LLOQ at end of treatment, confirmed with 2 consecutive values or last available posttreatment measurement
- Characterization of HCV drug resistance substitutions at baseline, during, and after therapy with LDV/SOF

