1.1.2. HCV Infection in Korea

In Korea, chronic HCV infection is one of the leading causes of chronic liver disease and hepatocellular carcinoma (HCC) {24211}. The age-standardized prevalence of HCV antibody (HCV Ab) in patients greater than 40 years of age is reported to be on the order of 1.3% which equates to around 193,000 people {24215}. The prevalence of HCV infection increases with age and peaks in those individuals aged 60 years and older {24211}. The majority of infections occurred via contaminated blood transfusions prior to the introduction of blood-donor HCV Ab screening in 1991 {24216}. Consequently the majority of patients with chronic hepatitis C in Korea are elderly {24215} and are more likely to have progressive liver disease. HCV infection is more closely associated with HCC in the elderly Korean patients than are HBV infection and alcoholism {24210}, {24208}. Since the decline of transfusion-related hepatitis C the majority of new infections are behavior-related. Of particular note is the practice of acupuncture for chronic illnesses including joint disease, pain, sequelae of trauma and other conditions non-responsive to conventional therapies. Shin et al reported results of a case study in which 34.1% of men and 62.9% of women in rural Korea reported multiple acupuncture procedures with the associated risk fraction for HCV infection being 38% for men and 55% for women {24214}. Intravenous drug abuse (IVDA) is not thought to be a major contributor to the overall prevalence of HCV infection in Korea however this route of infection may contribute in young adults and those living in harbor cities on the southern and western coasts {24209}, {24211}. The predominant HCV genotypes in Korea are GT-1b and GT-2a which are roughly present in equal proportions and combined account for around 80-90% of infections {24216}, {24215}, {24209}. Host IL28B genotype has been widely reported as a predictor of virologic response to interferon (IFN)-based therapies for chronic HCV infection {22075}. The IL28B-CC genotype which confers a favorable virologic outcome to IFN-based therapy predominates in Korea with approximately 80-90% of patients with this genotype {24212}, {24238}. Consequently the sustained virologic response rates in Korean clinical trials evaluating Peg-IFN α +RBV in treatment-naïve GT-1 infection are on the order of 55-70% following 48 weeks of therapy {24211}, {24595}, {24387}, {24385}, {24237}, {24404}, {24388}. Although relatively high rates of virologic response are achievable with Peg-IFN α +RBV in treatment-naïve Korean patients due to the high proportion of IL28B CC genotype, Heo et al {24236} recently reported a significant difference in SVR rate observed in a clinical trial cohort versus that observed in clinical practice based upon ‘Intention To Treat’ (ITT) analysis; 81% (21/26) versus 55% (58/106). Although no difference was observed in the SVR rates between the clinical trial cohort and the clinical practice cohort according to per protocol analysis, the ITT is important since it more likely reflects the observed SVR in clinical practice across the country. The authors attribute the lower ITT SVR rate in the clinical practice cohort to decreased adherence to assigned therapy including dose reduction for clinical and laboratory adverse events. As previously described, the highest prevalence rates for HCV Ab in Korean patients are in those individuals aged 60 years and older. These elderly patients are more likely to be treatment-experienced and have progressive liver disease. Comorbid conditions (e.g., diabetes and cardiovascular disease) are common in this population and pose significant

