1.1.4. HCV Infection in China

Reports indicate that around 2% of the population in China, or approximately 27 million people, may be infected with the hepatitis C virus {19682}, {24217}, {25129}. Approximately 68% of patients are infected with HCV GT-1b, 14% with GT-2, 4% with GT-3 and 13% with GT-6 {19682}, {24217}. GT-1 and GT-2 infection are generally more common in older patients whereas GT-3 and GT-6 are more frequent in younger adults. This observation may be related to the mode of HCV transmission, with GT-1/GT-2 commonly acquired through prior blood transfusion and GT-3/GT-6 associated with IVDA {25094}.

Risk factors for HCV infection are similar to those reported in other parts of the world {25095}. Of note, however, is the reported risk of acquiring transfusion-related HCV infection which is on the order of 1 in 40,000-60,000 donations {25093}. Such high rates of transfusion-related hepatitis C have been attributed in part to the practice of paid blood donation. Following introduction of mandatory HCV screening of blood/blood products in the 1990's and the implementation of the blood donation law in 1998, the incidence of post-transfusion hepatitis C has been significantly reduced {24392, 25127}. The association of GT-1 infection with blood transfusion and the timing of the new requirements related to blood donation may in part explain the higher GT-1 infection rates in the elderly. Since the introduction of blood-bank screening, the predominant mode of new HCV infection is now intravenous drug use (IDU).

The recommended treatment regimen for treatment-naïve patients with HCV GT-1 in China according to the Chinese Society of Hepatology {24428} is subcutaneous or intramuscular administration of IFN α or Peg-IFN α plus orally administered RBV for 24 to 48 weeks according to baseline viral load and virologic response. These recommendations are aligned with those by the APASL Consensus Committee {24699}, {22156}. SVR rates in China for GT-1 have been reported to be on the order of 44% to 70% {24797}, {13261}, {24391}.

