6.6.7. Viral RNA Sequencing / Phenotyping Sample

Plasma samples will be collected at Baseline/Day 1 and each additional visit for viral sequence analysis. At any unscheduled visit initiated for the purpose of confirming virologic breakthrough, a plasma sample for viral sequence analysis must be collected. Untested samples may be archived.

Details regarding the collection, processing, and shipping of samples will be included in the lab manual.

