For the SVR12 endpoint analysis, a summary table of the number and percentage of subjects with SVR12, virologic failure (VF), and Other will be created by prior treatment experience. All subjects who achieve SVR12 will be categorized as SVR12. Virologic failure will be descriptively summarized as “on-treatment virologic failure” and relapse (which will be summarized by study drug completed yes/no). Subjects who do not achieve SVR12 and do not meet criteria for VF will be categorized as “Other”. The denominator for relapse will be the number of subjects who had HCV RNA < LLOQ on their last observed on-treatment HCV RNA measurement; otherwise, the denominator will be the number of subjects in the FAS.

Drug resistant substitutions will be analyzed as part of the Virology Study Report.

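### Relapse is defined by HCV RNA alone, so a reinfection in a subject without SVR12 would be filed as relapse; the effect is one-directional, probably small, and leaves the primary SVR12 test unchanged

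*SAP*

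**What the plan says.** **Relapse.** SAP 6.2.1 defines relapse as an HCV RNA result at or above "LLOQ during the posttreatment period having achieved HCV RNA < LLOQ at end of treatment, confirmed with 2 consecutive values or last available posttreatment measurement". The source of the virus plays no part.

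**Outcome categories.** SAP 6.2.2 sets three: SVR12, virologic failure (on-treatment failure or relapse) and Other. Two rules fix the order: "All subjects who achieve SVR12 will be categorized as SVR12", and "Subjects who do not achieve SVR12 and do not meet criteria for VF will be categorized as “Other". On the rate itself, "The denominator for relapse will be the number of subjects who had HCV RNA < LLOQ on their last observed on-treatment HCV RNA measurement".

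**Samples.** Protocol 6.6.7: "Plasma samples will be collected at Baseline/Day 1 and each additional visit for viral sequence analysis". Protocol 6.4.9 makes a sample mandatory at any visit held to confirm virologic failure. The footnote to the post-treatment table in Protocol Appendix 2 says this plasma is stored for possible sequencing. HCV genotype and subtype are determined at Screening (Protocol 6.2.1 and 6.6.1). The only use of sequence data that the SAP names is resistance: "Drug resistant substitutions will be analyzed as part of the Virology Study Report".

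**New infection.** Protocol 1.1.4 gives injecting drug use as the main current route of new infection in China. For Korea, Protocol 1.1.2 says: "Since the decline of transfusion-related hepatitis C the majority of new infections are behavior-related". No listed exclusion criterion names drug use or continuing exposure. No readable section of either document mentions reinfection.

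**The concern.** Relapse is read as failure of the drug to clear the original virus. A second infection after clearance is a different event, but the two rules in SAP 6.2.2 leave it nowhere else to go. If it causes the subject to miss SVR12 and meets the relapse wording, Other is barred and relapse is the only label left. This is a stated rule that gives a wrong classification, not merely a detail left out.

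The stake is the relapse rate, a named secondary endpoint, and the reading of the few failures likely to occur. The protocol's earlier data show few subjects without SVR12: 0 of 171 on the same regimen in Japan (Section 1.2.2.3), and 109 − 102 = 7 of 109 treatment-experienced subjects in the international programme (Section 1.3). With counts this low, a single subject is visible in the table.

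**Working it through.** **The plan's own figures.** The documents state no relapse or reinfection rate, so there is none to reproduce. The nearest stated figure is the power for treatment-naive subjects in China (N = 100, 57% against 74%, two-sided exact test at 0.05). It reproduces: rejection on the upper side needs at least 68 responders, the upper-tail probability at 57% is 0.0160, and power at 74% is 0.928, against a stated minimum of 90%. The point below does not change it, because a reinfected subject is non-SVR12 before and after the fix.

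**Step 1: who is caught.** From SAP 6.2.1 and 6.2.2 together, a reinfected subject lands in the relapse row if all of these hold:
- HCV RNA was below LLOQ at end of treatment;
- SVR12 was not achieved;
- the post-treatment result at or above LLOQ is confirmed by a second consecutive value, or is the last one available.

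An isolated result at or above LLOQ followed by one below it is not relapse. Viraemia that first appears after SVR12 fits the 6.2.1 wording, which covers the whole post-treatment period. The outcome summary nevertheless keeps that subject as SVR12. The two sections do not agree on this subject.

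**Step 2: effect of one case.** Change in rate = 1 / denominator. The exact (Clopper-Pearson) 95% intervals are added for scale.

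| Denominator | No case | One case | Shift |
|---|---|---|---|
| 100 (China, one treatment-history group) | 0% (0 to 3.62) | 1% (0.03 to 5.45) | 1.0 point |
| 200 (China) | 0% (0 to 1.83) | 0.5% (0.01 to 2.75) | 0.5 point |
| 360 (Overall) | 0% (0 to 1.02) | 0.28% (0.01 to 1.54) | 0.28 point |

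These use planned enrolment. The SAP denominator leaves out subjects not below LLOQ at their last on-treatment result, so the true shift is at least this large.

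**Step 3: expected number of cases.** Assumption: a constant reinfection rate r between 0.1 and 10 per 100 person-years. The range is mine. Probability per subject by day d = 1 − exp(−(r/100) × d/365.25), multiplied by N = 200 (China).

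For r = 1 and d = 84: 1 − exp(−0.01 × 84/365.25) = 0.0023, and 200 × 0.0023 = 0.46.

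| r per 100 person-years | By Week 12 (84 days) | By Week 24 (168 days) |
|---|---|---|
| 0.1 | 0.05 | 0.09 |
| 1 | 0.46 | 0.92 |
| 5 | 2.29 | 4.55 |
| 10 | 4.55 | 8.99 |

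Week 12 is the nominal horizon for the outcome table. The analysis window for that visit runs to day 146 and takes the latest record (SAP 3.7.2 and 3.7.3), which gives 0.80 cases at r = 1. Week 24 is the relevant column if viraemia after SVR12 is also counted as relapse.

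**The case against.** The strongest case against is that the omission is narrow and the present rule errs against the drug. Several stronger conclusions that a reader might draw are not supported:

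- **That any post-treatment result at or above LLOQ is relapse.** The end-of-treatment and confirmation conditions rule this out.
- **That every reinfection in the 24-week follow-up enters the relapse row.** SVR12 takes precedence in the outcome summary, which roughly halves the nominal period.
- **That this cohort is at high risk.** The statements on new infection are population epidemiology. Protocol 1.1.4 links drug use in China with genotypes 3 and 6, and genotype 1 with past transfusion; only genotype 1 is enrolled. Protocol 1.1.2 does not regard injecting drug use as a major contributor in Korea overall. The criteria on general health and compliance may also remove some exposed subjects.
- **That reinfection would be a large share of relapses.** The earlier failure counts are all subjects without SVR12, not relapses, and no reinfection rate is documented.
- **That the resistance data are contaminated.** That analysis sits in a Virology Study Report whose plan is not supplied, and the SAP's exploratory sections are redacted. A Baseline-to-failure comparison may be specified there.

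All of this stands, and it limits the size of the point. It does not remove it, because the readable text still forces the wrong label. The genotype argument also cuts both ways: a genotype 3 or 6 infection would be easy to recognise and plainly wrong to report as relapse of genotype 1.

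One further warning stands. Treating any difference in subtype as reinfection could take true relapses out. Protocol 8.2.1.1 admits mixed 1a/1b infection, so a minority strain present at Baseline could re-emerge. In an open-label study that error would favour the drug.

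**Conclusion.** The concern holds in a limited form. Under SAP 6.2.1 and 6.2.2, a reinfected subject who misses SVR12 and meets the relapse wording is reported as a relapse. The bias can only be upward, at 1 point per case in 100 or 0.5 in 200. The number of cases is probably small: about half a case by Week 12 in China at an assumed 1 per 100 person-years, and between 0.05 and 4.55 across the assumed range. The endpoint is secondary and descriptive. The SVR12 rate, its exact test and the stated power do not change, provided reinfections stay non-SVR12. The change is worth making because it is cheap, but it has low priority.

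**What to change.** In SAP 6.2.1, 6.2.2 and Table 10 (virologic outcome):

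1. For each subject who meets the relapse wording, compare Baseline and failure-visit virus using the plasma already collected.
2. Keep all such subjects as non-SVR12, and keep relapse as now defined for the main row.
3. Add a line for sequence-confirmed reinfection: a different genotype, or virus phylogenetically distinct from Baseline and not explained by a mixed or minority Baseline strain. Show relapse with and without these cases.
4. Count unsequenced or indeterminate cases as relapse.
5. Flag reinfections in the resistance summary, or cross-refer to the Virology Study Report if it already does so.
6. State whether viraemia first appearing after SVR12 counts as relapse, so that 6.2.1 and 6.2.2 agree and the SVR12/SVR24 concordance table (Table 9) can be interpreted.

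The cost is SAP wording and one table line, with no new sampling. The line must wait for sequence results, and stored plasma would have to be sequenced for any failure not already covered. Subjects in Korea and Taiwan were analysed under the SAP of 22 July 2014, so any relapses already reported there need the same check before they enter the Overall column.

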6.2.2. Analysis Methods for Secondary Efficacy Endpoints

For analyses of HCV RNA < LLOQ by visit while on treatment and during the post-treatment (SVR) follow-up period, subjects will be assigned a value at each visit based on the categorical imputation rules described in Section 3.5. The 2-sided 95% exact confidence interval based on Clopper-Pearson exact method will be provided for the proportion by prior treatment experience for China and Overall {Clopper 1934}. The “HCV RNA < LLOQ” category will be split into the following 2 subcategories: “< LLOQ TND” for subjects with target not detected and “< LLOQ detected” for subjects with < LLOQ in tabular displays.

Graphs for the proportion of subjects with HCV RNA < LLOQ over time during treatment will be displayed.

Summary statistics will be presented for absolute values and change from baseline in HCV RNA (\log_{10} IU/mL) by visit and by prior treatment experience through Week 12 in China. Since LLOQ is 15 IU/mL of COBAS[®] AmpliPrep/COBAS[®] TaqMan[®] HCV Test v2.0 used to determine HCV RNA results of China, while LLOQ is 25 IU/mL of the COBAS[®] Taqman[®] HCV Test v2.0 for use with the High Pure System used in Korea and Taiwan, summary statistics for absolute values and change from baseline in HCV RNA for Overall (ie, China, Korea, plus Taiwan) will not be provided. Results for Korea and for Taiwan using the LLOQ of 25 IU/mL have been reported separately in the GS-US-337-0131 interim CSR dated 10 October 2014. Imputation rules described in Section 3.5 will be used to assign HCV RNA values for missing values at a visit that are bracketed by “< LLOQ TND” and/or “< LLOQ detected”. Otherwise, a missing = excluded analysis will be performed. Plots of the mean \pm SD and median (Q1, Q3) of absolute values and changes from baseline in HCV RNA through Week 12 for subjects in China will be presented.

For the SVR12 endpoint analysis, a summary table of the number and percentage of subjects with SVR12, virologic failure (VF), and Other will be created by prior treatment experience. All subjects who achieve SVR12 will be categorized as SVR12. Virologic failure will be descriptively summarized as “on-treatment virologic failure” and relapse (which will be summarized by study drug completed yes/no). Subjects who do not achieve SVR12 and do not meet criteria for VF will be categorized as “Other”. The denominator for relapse will be the number of subjects who had HCV RNA < LLOQ on their last observed on-treatment HCV RNA measurement; otherwise, the denominator will be the number of subjects in the FAS.

Drug resistant substitutions will be analyzed as part of the Virology Study Report.

